13.5.5.3 Subject Hospital Discharge

The proportion of subjects to be discharged alive from the hospital, through day 28, will be summarized using descriptive statistics (totals and percentages) for subjects overall and by treatment group. The estimand of the proportion of hospital discharge will be calculated by treatment group, along with 95% confidence intervals. A chi-square test will be used to test the significance in the proportion of subjects who are discharged between the INOpulse and placebo treatment groups.

13.5.5.4 Subject Hospital Duration

Subject hospital duration will be defined as the time from Day 1 (start of study treatment) to the day of hospital discharge or Day 28 of treatment for patients who are still hospitalized. If a patient has expired on or before Day 27 of treatment, they will be assigned a value of 28 days. Duration of hospital stay will be summarized (n, mean, std, median, Q1, Q3, minimum, and maximum) overall and by treatment group. The estimand of the median hospital duration will be summarized by treatment group, along with 95% confidence intervals. The non-parametric Mann-Whitney test will be used to test the difference in the duration of hospital stay between the two treatment groups.

13.5.5.5 Mortality

All-cause mortality will be defined as death from any cause through day 28 (treatment day 27). The all-cause mortality will be summarized using proportions, with all subjects in the ARAS included in the denominator.

Disease-specific mortality will be defined as death due to cardiopulmonary causes through day 28 (treatment day 27). This will be defined as having an adverse event under the respiratory body system/SOC, with outcome of death. It will be summarized using proportions, but the denominator will be the FES, excluding [subjects with] other causes of death through day 28.

Mortality rates will be displayed overall and by treatment group, age group, and gender as a subgroup analysis. The estimand of the proportion of mortality will be calculated by treatment group, along with 95% confidence intervals. A chi-square test will be used to test the significance in the proportion of mortality between the iNO and placebo treatment groups.

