9.0 Study Endpoints

Objectives	Endpoints
Primary	Primary endpoint

 The primary objective in this study is to verify the efficacy of INOpulse in subjects with COVID-19. 	
 Proportion of subjects who died or had respiratory failure (DRF as defined in Section 10.0 below) through Day 28.
	Secondary Endpoints
	
 8-point NIAID ordinal scale (Table 2 below) assessed at Day 7, 14, 28 and day of discharge. Proportion of subjects to recover, defined as return to room air or baseline oxygen requirements, or discharged alive from hospital [Through Day 28]. Proportion of subjects discharged alive from hospital [Through Day 28] Duration of hospitalization [Through Day 28]. Mortality [Through Day 28]: 
 All-cause mortality Cardiopulmonary mortality Proportion of subjects with a negative conversion of RT-PCR from a nasopharyngeal or bilateral nasal swab [through Day 28].
Secondary	
 The secondary objective in this study is to evaluate the safety of INOpulse in subjects with COVID-19.
	
 Proportion of subjects with adverse events leading to study drug discontinuation [Through Day 28].

Table 2: 8-Point NIAID Ordinal Scale

Score	Outcome
1	Death
2	Hospitalized, requiring mechanical ventilation or ECMO
3	Hospitalized, requiring non-invasive ventilation or high flow oxygen
4	Hospitalized, requiring supplemental oxygen
5	Hospitalized, not requiring supplemental oxygen - requiring ongoing medical care (COVID-19 related or otherwise)
6	Hospitalized, not requiring supplemental oxygen - not requiring ongoing medical care (COVID-19 related or otherwise)
7	Not hospitalized - limitation on activities and/or requiring home oxygen
8	Not hospitalized, no limitations on activities

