11.3 Full Efficacy Set

The Full Efficacy Set (FES) includes all randomized, COVID-confirmed subjects who received any amount of study drug. Note that subjects who began study treatment with high suspicion of COVID infection but subsequently had negative test results on the RT-PCR swab – will be excluded from FES.

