13.5.5 Secondary Endpoints

Secondary efficacy analyses will be performed on the secondary endpoints using the subjects in the ARAS.

Summary measures of the secondary endpoints (i.e. totals, means, proportions) will also be calculated for the following subgroups: race, gender, age group (≤ 65 years vs > 65 years), and baseline disease severity (oxygen ≤ 5 vs > 5 and comorbidities < 2 or ≥ 2).

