Table 14.2.2.5.5	Summary and Analysis of Hospital Duration by No. of Co-Morbidities	All Randomized Analysis Set
Table 14.2.2.6	All-Cause Mortality	All Randomized Analysis Set
Table 14.2.2.6.1	All-Cause Mortality by Race	All Randomized Analysis Set
Table 14.2.2.6.2	All-Cause Mortality by Gender	All Randomized Analysis Set
Table 14.2.2.6.3	All-Cause Mortality by Age Group	All Randomized Analysis Set
Table 14.2.2.6.4	All-Cause Mortality by Baseline Oxygen Level	All Randomized Analysis Set
Table 14.2.2.6.5	All-Cause Mortality by No. of Co-Morbidities	All Randomized Analysis Set

Table Number	Title	Population
Table 14.2.2.7	Disease-Specific Mortality	All Randomized Analysis Set
Table 14.2.2.7.1	Disease-Specific Mortality by Race	All Randomized Analysis Set
Table 14.2.2.7.2	Disease-Specific Mortality by Gender	All Randomized Analysis Set
Table 14.2.2.7.3	Disease-Specific Mortality by Age Group	All Randomized Analysis Set
Table 14.2.2.7.4	Disease-Specific Mortality by Baseline Oxygen Level	All Randomized Analysis Set
Table 14.2.2.7.5	Disease-Specific Mortality by No. of Co-Morbidities	All Randomized Analysis Set
Table 14.2.2.8	Summary of RT-PCR Results by Time Point	All Randomized Analysis Set
Table 14.2.2.8.1	Summary of RT-PCR Results by Time Point by Race	All Randomized Analysis Set
Table 14.2.2.8.2	Summary of RT-PCR Results by Time Point by Gender	All Randomized Analysis Set
Table 14.2.2.8.3	Summary of RT-PCR Results by Time Point by Age Group	All Randomized Analysis Set
Table 14.2.2.8.4	Summary of RT-PCR Results by Time Point by Baseline Oxygen Level	All Randomized Analysis Set
Table 14.2.2.8.5	Summary of RT-PCR Results by Time Point by No. of Co-Morbidities	All Randomized Analysis Set
Table 14.2.2.9	Difference in Proportion in RT-PCR Results at Discharge by Treatment Group	All Randomized Analysis Set
Table 14.3.1.1	Summary of Exposure	Full Efficacy Set
Table 14.3.2.1	Overall Summary of Treatment-Emergent Adverse Events	Full Safety Set
Table 14.3.2.2	Treatment-Emergent Adverse Events by System Organ Class and Preferred Term	Full Safety Set
Table 14.3.2.3	Serious Treatment-Emergent Adverse Events by System Organ Class and Preferred Term	Full Safety Set
Table 14.3.2.4	Treatment-Emergent Adverse Events Leading to Discontinuation of IP by System Organ Class and Preferred Term	Full Safety Set
Table 14.3.2.5	Treatment-Emergent Adverse Events with Outcome of Death by System Organ Class and Preferred Term	Full Safety Set

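### Cardiopulmonary mortality is derived from fatal respiratory-SOC events only, and its denominator conflicts with the ARAS that the SAP specifies elsewhere for the same endpoint

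*SAP*

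**What the plan says.** Protocol 7.2 and SAP 9.0 both list "Cardiopulmonary mortality" through Day 28 as a component of the fifth secondary endpoint. The protocol gives no derivation. SAP 13.5.5.5 supplies one in three steps.

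- Concept: "Disease-specific mortality will be defined as death due to cardiopulmonary causes through day 28 (treatment day 27".
- Numerator: "This will be defined as having an adverse event under the respiratory body system/SOC, with outcome of death".
- Denominator: "the denominator will be the FES, excluding [subjects with] other causes of death through day 28".

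The arms are then compared by chi-square, and SAP 13.5.2 places the secondary endpoints in a hierarchical sequence that follows the order of 13.5.5.

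The population is stated differently elsewhere. SAP 13.5 puts the efficacy endpoints on the ARAS, and SAP 13.5.5 says "Secondary efficacy analyses will be performed on the secondary endpoints using the subjects in the ARAS". Appendix 4 gives the All Randomized Analysis Set as the population for Table 14.2.2.7, titled "Disease-Specific Mortality", and for its five subgroup tables. All-cause mortality, in the same section as the rule at issue, is summarised "with all subjects in the ARAS included in the denominator". The two sets differ: the ARAS is everyone randomised, whereas "The Full Efficacy Set (FES) includes all randomized, COVID-confirmed subjects who received any amount of study drug".

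**The concern.** The numerator is narrower than the endpoint's name and than the concept stated one sentence earlier. No cardiac SOC, term list or cause-of-death review appears for this endpoint, so a programmer who follows the rule reports a respiratory death rate under a cardiopulmonary title.

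The denominator raises two separate problems. First, the FES in 13.5.5.5 and the ARAS in Appendix 4 cannot both be the population of Table 14.2.2.7. Second, removing subjects because they died of something else conditions the comparison on a post-randomisation outcome, which departs from the intent-to-treat approach that SAP 13.5.1 adopts for the primary estimand. The phrase for other causes is also undefined. If it means non-respiratory, a cardiac-only death leaves the denominator. If it means non-cardiopulmonary, that subject stays in as a non-event.

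At stake is the result of a formally tested secondary endpoint on which events are likely to be few, so that a handful of misallocated deaths can move the estimate.

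**Working it through.** **No plan figure to reproduce.** The documents state no rate, power or sample size for this endpoint. The only death count is in the expanded-access summary (Protocol 5): 1 death among 22 COVID-positive patients, uncontrolled and with no cause given. Every death count below is therefore an assumption.

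**Inputs.** 500 subjects randomised 1:1 (SAP 8.1), so 250 per arm. Assumed respiratory deaths are 6 (iNO) v 12 (placebo). Cardiac-only deaths are varied. The test is Pearson chi-square without continuity correction; differences are iNO minus placebo.

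**Formulas.**
- Intended rate = (respiratory + cardiac-only deaths) / ARAS.
- SAP rate, reading 1 = respiratory deaths / (FES − cardiac-only − other deaths).
- SAP rate, reading 2 = respiratory deaths / (FES − other deaths), with cardiac-only deaths kept as non-events.

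**Step 1: numerator, holding FES = ARAS = 250 and no other deaths.**

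| Cardiac-only deaths, iNO v placebo | Intended | SAP, reading 1 | SAP, reading 2 |
|---|---|---|---|
| 3 v 3 | 9/250 v 15/250 = 3.60% v 6.00%; −2.40; p = 0.21 | 6/247 v 12/247 = 2.43% v 4.86%; −2.43; p = 0.15 | 6/250 v 12/250 = 2.40% v 4.80%; −2.40; p = 0.15 |
| 4 v 2 | 10/250 v 14/250 = 4.00% v 5.60%; −1.60; p = 0.40 | 6/246 v 12/248 = 2.44% v 4.84%; −2.40; p = 0.155 | −2.40; p = 0.15 |
| 2 v 4 | 8/250 v 16/250 = 3.20% v 6.40%; −3.20; p = 0.094 | 6/248 v 12/246 = 2.42% v 4.88%; −2.46; p = 0.145 | −2.40; p = 0.15 |

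When cardiac deaths are balanced, both rates fall by about 1.1 to 1.2 points and the difference hardly moves. With a two-death imbalance the difference shifts by 2.40 − 1.60 = 0.80 points towards iNO, or by 3.20 − 2.46 = 0.74 to 3.20 − 2.40 = 0.80 points against it.

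**Step 2: FES against ARAS.** Assume no cardiac or other deaths, an FES at 90% of the ARAS (0.90 × 250 = 225 per arm), and every respiratory death inside the FES. ARAS: 6/250 v 12/250, difference −2.40, p = 0.150. FES: 6/225 = 2.67% v 12/225 = 5.33%, difference −2.67, p = 0.149. The rates and the difference are scaled up by 1/0.90; the test barely changes. Deaths among subjects outside the FES are not modelled.

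**Step 3: direction within one arm.** Assume 10 respiratory deaths and 1 cardiac-only death, with an FES of 225. SAP reading 1 gives 10/(225 − 1) = 4.46%, against an intended 11/250 = 4.40%, so the reported rate is slightly too high. With 10 respiratory, 5 cardiac-only and 2 other deaths and an FES of 250, it gives 10/243 = 4.12% against 15/250 = 6.00%, so it is too low.

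**Step 4: are the counts plausible?** The intended counts of 8 to 10 v 14 to 16 lie below the planned death-or-respiratory-failure counts of 0.06 × 250 = 15 and 0.15 × 250 = 37.5. They may still be high. In expanded access 1 of 3 deteriorations was fatal, and one third of 15 is about 5 deaths on iNO.

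**The case against.** The strongest reply is that little turns on this. Cardiac-only deaths may be rare: Protocol 8.3 excludes systolic heart failure with LVEF below 40%, hypotension unresponsive to vasopressors, and proven pulmonary embolus. Protocol 13.1.5 makes protocol-defined respiratory failure an SAE, so many deaths will carry a respiratory event. The ventricular fibrillation and cardiac arrest entries in SAP 13.6.2 are there as rebound effects of acute withdrawal. These points limit the likely number of affected deaths. They do not make the rule match the endpoint, and the SAP still lists left heart failure as an event of special interest and stratifies on comorbidities that include cardiovascular disease.

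On the denominator, the wording of 13.5.5.5 contrasts the FES with the all-cause rule and may be a deliberate exception to the general ARAS statement. That could reconcile it with 13.5 and 13.5.5. It cannot explain why Appendix 4 assigns this endpoint's own tables to the ARAS, nor does it justify excluding subjects on outcome.

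The deaths are also visible elsewhere. Table 14.3.2.5 shows treatment-emergent fatal events by SOC in the Full Safety Set, and Listing 16.2.7.3 gives death details for all randomised subjects. A reader could find the uncounted deaths, but the tested result would not be corrected.

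A reader might infer that the reported rate is too low in every arm with a cardiac-coded death. The documents do not support that: subjects with fatal events in both SOCs are counted, and the smaller FES can outweigh the loss, as step 3 shows. A reader might also infer that the rule could reverse the trial's conclusion. Nothing in the documents supports that either.

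**Conclusion.** The rule is wrong as written, in a limited way. The numerator does not deliver the endpoint that the protocol and SAP name, and the denominator contradicts the population of the endpoint's own tables. Both conclusions rest on the text alone.

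The size rests on assumed counts. With 250 per arm and 6 v 12 respiratory deaths, an imbalance of two cardiac-only deaths moves the difference by about 0.7 to 0.8 points. An FES at 90% of the ARAS moves it from −2.40 to about −2.67 with p still near 0.15. No illustrated case crosses 0.05, and the net direction of the error in a single arm's rate is not fixed.

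The consequence is confined to one component of the fifth-ranked secondary endpoint, which is tested only if the primary and the earlier secondaries succeed. The primary endpoint and all-cause mortality are unaffected. It should be corrected, but it does not threaten the main result.

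**What to change.** Amend SAP 13.5.5.5 before unblinding.

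- Numerator: count each subject once if a death through Day 28 has a fatal adverse event in the respiratory or cardiac SOC. List in advance any further cardiopulmonary preferred terms that are coded to other SOCs, because the documents do not show that these two SOCs capture every such death.
- Denominator: all ARAS subjects by randomised arm, with other-cause deaths kept as non-events. This choice follows 13.5, 13.5.5 and Appendix 4, and it removes the need to define other causes for the denominator.
- Align 13.5.5.5 with 13.5, 13.5.5 and Tables 14.2.2.7 to 14.2.2.7.5.

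The cost is SAP wording and a short blinded review of preferred terms. Adverse events are collected for randomised subjects from consent (Protocol 13.4.1), so undosed ARAS subjects can be included. Fatal events by SOC are already a planned output. No new data, visits or subjects are needed.

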13.5.5.6 RT-PCR Conversion

Confirmation of COVID-19 diagnosis will be done through RT-PCR testing. Samples will be taken at baseline and End of Treatment/discharge. RT-PCR results will be summarized as positive or negative using proportions, overall and by treatment group; this will be done in the ARAS dataset, which by definition requires positive at baseline. Among subjects who had a positive RT-PCR test at study enrollment, the test positivity rate at hospital discharge will be calculated by treatment group, along with 95% confidence intervals. A chi-square test will be used to test the significance in the proportion of positivity between the INOpulse and placebo treatment groups at discharge. Death will be imputed as a positive conversion even in the case the subject was a negative conversion and died.

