COVID-19 infection must be confirmed via positive RT-PCR, or have high index of suspicion of infection with results pending. Upon successful completion of screening, subjects will receive treatment with placebo or iNO 125 mcg/kg IBW/hr up until resolution of hypoxemia, protocol defined respiratory failure, hospital discharge or Day 28, whichever occurs first. In instances where continuous INOpulse dosing is not feasible (eg, due to PPE limitations), INOpulse should be used a minimum of 12 hours daily.

Prior to randomization, the following screening assessments (0 to -14 days prior to randomization) will be completed as described in **Table 2**:

- Informed consent
- COVID-19 RT-PCR obtained from an upper respiratory tract specimen within the previous 4 days. Subjects may be positive for COVID-19 or have high suspicion of infection at the time of randomization with RT-PCR results pending. If a subject is randomized based upon a high suspicion of COVID-19 infection and the swab RT-PCR comes back negative, a repeat RT-PCR swab can be taken and the subject can be continued on INOpulse pending the repeat results. If the repeat RT-PCR results come back negative, the subject should be discontinued from INOpulse therapy. If the subject deteriorates after discontinuation of INOpulse, the Investigator should consider the reintroduction of INOpulse therapy.
- CT scan or chest x-ray after onset of symptoms and within 14 days of randomization
- CBC with differential, chemistry panel (sodium, potassium, chloride, CO₂, BUN, creatinine, glucose), LFTs (AST/ALT and total bilirubin), triglycerides, troponin (High Sensitivity Cardiac Troponin [HS-cTN]), procalcitonin, ferritin, fibrinogen, D-dimer NT-proBNP and LDH. If available locally, CRP, Von Willebrands Factor, Factor VIII Activity, Protein C, Protein S, Homocysteine, Antithrombin 3, Thrombelastography (TEG), G6PD deficiency and Prothrombin gene G2021A. Lab results obtained within the previous 48 hours are acceptable for screening purposes if there has not been a significant change in the subject's clinical status.
- Pregnancy test (urine or serum) for women of child-bearing potential
- Vital signs (heart rate, respiratory rate, blood pressure, temperature)
- Oxygen saturations
- Document oxygen flow requirements
- Medical History including a documented reason for hospital admission
- Physical exam
- Review inclusion and exclusion eligibility criteria

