8.2. Inclusion Criteria

Subjects must meet all of the following inclusion criteria to be enrolled and eligible to participate in the study:

1. Signed Informed Consent Form (and assent as appropriate) prior to the initiation of any study mandated procedures or assessments.
2. At least 18 years old
3. [REMOVED IN AMENDMENT #1]
4. Subject must be hospitalized and have the following:
 - proven or high suspicion of SARS-CoV-2 infection, and
 - requiring oxygen supplementation defined as:
 - $\text{SpO}_2 \leq 92\%$ regardless of supplemental oxygen (ie on room air or on oxygen); or
 - $\text{SpO}_2 \geq 92\%$ on supplemental O₂ and in the opinion of the Investigator it is not safe to decrease or remove the supplemental oxygen
 - require supplemental oxygen of no more than 10 L/minute, and
 - radiologic suspicion or proof of COVID-19 pneumonitis (chest x-ray or CT scan)
5. Female subjects of childbearing potential must have a negative pre-treatment pregnancy test (serum or urine). All female subjects should take adequate precaution to avoid pregnancy.
6. Willing and able to comply with treatment schedule and study procedures.

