11.0 Analysis Sets

11.1 All Randomized Analysis Set

The All Randomized Analysis Set (ARAS) includes all subjects who are randomized in the study. That is the primary analysis set for by-subject listings.

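### SAP 13.5.5.6 wrongly says ARAS requires a positive baseline RT-PCR, which leaves the denominator of the between-arm RT-PCR test open

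*SAP*

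**What the plan says.** SAP 13.5.5.6 describes the RT-PCR endpoint in three steps.

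- **Summary.** Results are summarised as positive or negative by arm, and "this will be done in the ARAS dataset, which by definition requires positive at baseline".
- **Rate.** The next sentence is narrower: "Among subjects who had a positive RT-PCR test at study enrollment, the test positivity rate at hospital discharge will be calculated", by arm and with 95% confidence intervals.
- **Test.** A chi-square test then compares positivity between the arms at discharge. This sentence names no denominator.

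SAP 11.1 says that ARAS "includes all subjects who are randomized in the study" and attaches no test condition. The set that does need confirmed infection is the Full Efficacy Set (FES), which "includes all randomized, COVID-confirmed subjects who received any amount of study drug". SAP 11.3 removes from FES the "subjects who began study treatment with high suspicion of COVID infection but subsequently had negative test results on the RT-PCR swab".

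The protocol's inclusion criterion 4 accepts "proven or high suspicion of SARS-CoV-2 infection, and" so proof is not required. The synopsis says: "Subjects may be positive for COVID-19 or have high suspicion of infection at the time of randomization with RT-PCR results pending".

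In SAP Appendix 4, the by-time-point summaries (Tables 14.2.2.8 to 14.2.2.8.5) and Table 14.2.2.9, "Difference in Proportion in RT-PCR Results at Discharge by Treatment Group", all carry the population label All Randomized Analysis Set.

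**The concern.** The endpoint in SAP 9.0 is negative conversion, which has meaning only for a subject who was positive to begin with. The SAP credits ARAS with a property that belongs to FES. A programmer who trusts that clause and the Table 14.2.2.9 label would apply no baseline filter. One who works from the rate sentence would apply it. The plan supports both readings for the one formal comparison on this endpoint, and that comparison sits in a hierarchy controlled at 5% (SAP 13.5.2). The denominator should be settled before results are seen.

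Never-positive subjects are also likely to have follow-up data. The protocol's schedule of assessments places an RT-PCR swab at End of Treatment and at Early Discontinuation. A subject randomised on suspicion and later found negative can therefore supply a negative follow-up result that is not a conversion.

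A second gap remains even if the filter is applied. Positive at enrolment is not defined for a swab that was pending at randomisation, nor for a subject who was first negative and then positive on the permitted repeat.

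**Working it through.** The documents give no conversion rate, no share of never-positive subjects and no power for this endpoint, so there is no figure of the plan's own to reproduce. The check is a comparison of definitions, followed by an illustration of size.

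**Step 1: is the premise true?**

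| Source | Positive test required? |
|---|---|
| SAP 13.5.5.6, on ARAS | Yes, said to follow by definition |
| SAP 11.1, ARAS | No, all randomised subjects |
| Protocol synopsis and 8.2 | No, high suspicion with the result pending is enough |
| SAP 11.3, FES | Yes, and dosing as well |

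The premise is false. The exclusion written into FES shows that the SAP expects some subjects to turn out negative. Nothing removes them from ARAS.

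**Step 2: which outputs are exposed?**

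| Output | Denominator in text | Label in Appendix 4 |
|---|---|---|
| Results by time point (14.2.2.8 and its subgroup tables) | ARAS | ARAS |
| Discharge positivity rate and intervals | Positive at enrolment | No separate shell |
| Chi-square test and difference (14.2.2.9) | Not stated | ARAS, no qualifier |

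Only the last row is in doubt for the formal comparison.

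**Step 3: how much could it matter?** Let f be the share of ARAS never positive, assumed equal in both arms and all negative at follow-up. Let p be the conversion rate among baseline positives. Then:

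- proportion negative in ARAS = f + (1 − f) × p
- difference between arms in ARAS = (1 − f) × true difference

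With assumed p of 40% and 30%, and f = 10%:

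- 0.10 + 0.90 × 0.40 = 0.46
- 0.10 + 0.90 × 0.30 = 0.37
- difference = 0.90 × 10 = 9 points

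A second assumed case uses 250 subjects per arm, true conversion of 42% and 30% (12 points), and a two-sided 5% test:

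| f | Subjects of 500 | Negative in the 30% arm, as shown in ARAS | Difference in ARAS | Power, all ARAS | Power, baseline positives only |
|---|---|---|---|---|---|
| 2% | 10 | 31.4% | 11.8 | 78% | 79% |
| 5% | 25 | 33.5% | 11.4 | 74% | 78% |
| 10% | 50 | 37.0% | 10.8 | 69% | 76% |
| 15% | 75 | 40.5% | 10.2 | 63% | 73% |

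If the true difference is zero, (1 − f) × 0 = 0 for every f. The unrestricted analysis dilutes a real difference and does not create a false one.

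**The case against.** The strongest reply is that the rate sentence already imposes the right restriction. The chi-square sentence follows it directly and is most naturally read as a test of that same rate. The population column in Appendix 4 is weak evidence against this, because it looks like a blanket label: SAP 13.5.5.5 gives disease-specific mortality an FES-based denominator, yet Table 14.2.2.7 is labelled ARAS as well. This reply stands in part. It rules out saying that the plan definitely tests conversion in uninfected subjects. It does not settle the matter, because the test sentence is silent, the shell has no qualifier, and the false clause tells the programmer that no filter is needed.

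A reader might also infer that Tables 14.2.2.8 to 14.2.2.8.5 misreport conversion. The documents do not support that. They are titled as results by time point, and a baseline-negative subject would appear there openly as negative at baseline.

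The illustration is an upper-end case for the shares and rates assumed. SAP 13.5.5.6 counts deaths as positive, so a never-positive subject who dies would not add a negative, and some follow-up swabs will be missing. This stands.

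Finally, RT-PCR conversion is listed last in SAP 13.5.5. Under SAP 13.5.2 it is tested only if the primary endpoint and every earlier secondary endpoint succeed. This also stands and limits the severity.

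**Conclusion.** The statement about ARAS in SAP 13.5.5.6 is an error, and it leaves the denominator of the chi-square test and Table 14.2.2.9 ambiguous. If the unrestricted reading were used, the negative rate would be inflated and a true difference modestly diluted: 9 points in place of 10 in the simplest illustration. All rates and shares behind these figures are assumptions, including an equal never-positive share in both arms with every such subject negative at follow-up.

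A reader might infer that the comparison is biased in favour of one arm. The documents do not support this. Infection status before treatment does not depend on allocation, so the expected share is the same in both arms, and the difference stays at zero when there is no effect. The primary analysis is untouched. Severity is minor.

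**What to change.** 1. Delete the clause saying that ARAS requires a positive baseline test.
2. State one denominator for the rate, the confidence intervals and the chi-square test, for example: *ARAS subjects whose RT-PCR sample collected before the first dose of study drug was positive, whenever the result was reported.* This settles the pending-swab question and agrees with the SAP 10.0 definition of baseline as the last assessment before first dose.
3. Put subjects who were positive only on a repeat swab taken after treatment started into a sensitivity analysis. The main denominator should not depend on an on-treatment result.
4. Label Table 14.2.2.9 with that subset. Table 14.2.2.8 and its subgroup tables may stay in ARAS as descriptions by time point, provided they are not presented as conversion.

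FES is the SAP's existing confirmed-infection set, but it also requires dosing. A subset of ARAS stays closer to the population that SAP 13.5.5 names for the secondary analyses.

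The cost is a few SAP sentences, one table label, one added sensitivity analysis and a slightly smaller denominator. In the assumed cases above, the smaller denominator does not reduce power relative to the unrestricted analysis.
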